5.1.2. Placebo-Controlled Period Final Analysis

In addition to the above described counts and percentages for the PCP Week 12 Analysis, the following counts and percentages of subjects will also be presented for the PCP Final Analysis:

- Completed PCP study treatment
- Did not complete PCP study treatment, including reasons for PCP study treatment discontinuation
- Completed PCP
- Did not complete PCP, including reasons for withdrawal from PCP

5.2. Major Protocol Deviations

Protocol deviations will be identified and reviewed on an ongoing basis by the study team and entered into a Clinical Trial Management System. Major protocol deviations are defined as those that can affect efficacy and/or safety assessments, the safety or mental integrity of a subject, or the scientific value of the study. Protocol deviations will be prospectively classified as major or minor.

The number and percentage of subjects with a major protocol deviation overall and for each major protocol deviation type will be summarized. In addition, COVID-19 related and non-COVID-19 related major protocol deviations will be summarized.

Protocol deviations will also be presented in a by-subject data listing.

In addition, subjects who were randomized in error and subjects who were mis-stratified (defined as subjects for whom the value of the randomization stratification factor, systemic corticosteroid use at baseline [yes/no], is different than the actual value of the stratification factor at randomization) will be presented in by-subject data listings.

6. DEMOGRAPHIC AND OTHER BASELINE CHARACTERISTICS

6.1. Demographic and Baseline Characteristics

The following demographic and baseline characteristics will be summarized:

- Age (years), both continuously and categorically (≥ 18 - < 50 , ≥ 50 - < 65 , ≥ 65)
- Sex (male, female)
- Race (American Indian or Alaska Native, Asian, Black or African American, Native Hawaiian or Other Pacific Islander, Other, White)
- Ethnicity (Hispanic or Latino, Not Hispanic or Latino)

- Weight (kg)
- Height (cm)
- Body mass index (BMI) (kg/m²), both continuously and categorically (< 18.5, ≥ 18.5 - < 25, ≥ 25 - < 30, ≥ 30)
- Region/Country (Australia, Europe [Czech Republic, Georgia, Italy, Moldova, Poland, Romania, Russia, Serbia, Ukraine], South Korea, and United States)

Demographic and baseline characteristics will also be presented in a by-subject data listing.

6.2. Baseline Disease Characteristics

The following baseline disease characteristics will be summarized:

- Extent of disease (left side of colon, extensive)
- Time since UC symptom onset (years), both continuously and categorically, using categories of < 1, ≥ 1 - < 3, ≥ 3 - < 7, and ≥ 7
- Time since UC diagnosis (years), both continuously and categorically, using the same categories as time since UC symptom onset
- Systemic corticosteroid use (yes, no)
 - Per randomization stratum
 - Actual value
- Systemic corticosteroid dependent
- Smoking history (current, former, never)
- Fecal calprotectin (mg/kg), both continuously and categorically (normal [< 50], high [≥ 50]; ≤ 250 , > 250; and ≤ 500 , > 500)
- Fecal lactoferrin (μ g/g), both continuously and categorically (normal [≤ 7.24], high [> 7.24])
- C-reactive protein (mg/L), both continuously and categorically (normal [≤ 5.0], high [> 5.0])
- UC-100 index

Baseline disease characteristics will also be presented in a by-subject data listing.

6.3. Baseline Mayo Score and Subscores

Baseline Mayo score and subscores will be summarized based on the following:

- Mayo score, both continuously and categorically
 - 0 - 2 (Quiescent disease), including individual categories of 0, 1, and 2
 - 3 - 5 (Mild disease), including individual categories of 3, 4, and 5
 - 6 - 10 (Moderate disease), including individual categories of 6, 7, 8, 9, and 10

- 11 - 12 (Severe disease), including individual categories of 11 and 12
- Mayo subscores, both continuously and categorically
 - Stool frequency subscore (SFS)
 - 0 (Normal number of stools)
 - 1 (1 - 2 stools more than normal)
 - 2 (3 - 4 stools more than normal)
 - 3 (5 or more stools than normal)
 - Rectal bleeding subscore (RBS)
 - 0 (No blood seen)
 - 1 (Streaks of blood with stool less than half the time)
 - 2 (Obvious blood with stool most of the time)
 - 3 (Blood alone passes)
 - Endoscopic subscore
 - 0 (Normal or inactive disease)
 - 1 (Mild disease [erythema, decreased vascular pattern])
 - 2 (Moderate disease [marked erythema, absent vascular pattern, friability, erosions])
 - 3 (Severe disease [spontaneous bleeding, ulceration])
 - Physician's Global Assessment (PGA)
 - 0 (Normal)
 - 1 (Mild disease)
 - 2 (Moderate disease)
 - 3 (Severe disease)
- Modified Mayo score, both continuously and categorically
 - 0 - 1 (Quiescent disease), including individual categories of 0 and 1
 - 2 - 4 (Mild disease), including individual categories of 2, 3, and 4
 - 5 - 7 (Moderate disease), including individual categories of 5, 6, and 7
 - 8 - 9 (Severe disease), including individual categories of 8 and 9
- Partial Mayo score, both continuously and categorically
 - 0 - 1 (Quiescent disease)

- 2 - 4 (Mild disease)
- 5 - 7 (Moderate disease)
- 8 - 9 (Severe disease)
- 6-Point Mayo score, both continuously and categorically
 - 0 (Quiescent disease)
 - 1 - 2 (Mild disease)
 - 3 - 4 (Moderate disease)
 - 5 - 6 (Severe disease)
- Reference normal stool frequency (number of stools per day), continuously and categorically
 - When in remission
 - Prior to UC symptom onset/diagnosis

Baseline Mayo scores and subscores will also be presented in a by-subject data listing.

6.4. Baseline Histologic Activity

Baseline histologic activity will be summarized based on the following:

- RHI, both continuously and categorically
 - 0 - 3 (Quiescent)
 - 4 - 10 (Mild)
 - 11 - 18 (Moderate)
 - 19 - 33 (Severe)
- RHI subscores, both continuously and categorically
 - Chronic inflammatory infiltrate RHI subscore
 - 0 (No increase)
 - 1 (Mild but unequivocal increase)
 - 2 (Moderate increase)
 - 3 (Marked increase)
 - Lamina propria neutrophils RHI subscore
 - 0 (None)
 - 1 (Mild but unequivocal increase)
 - 2 (Moderate increase)

- 3 (Marked increase)
- Neutrophils in epithelium RHI subscore
 - 0 (None)
 - 1 (< 5% crypts involved)
 - 2 (< 50% crypts involved)
 - 3 (> 50% crypts involved)
- Erosion or ulceration RHI subscore
 - 0 (No erosion, ulceration or granulation tissue)
 - 1 (Recovering epithelium + adjacent inflammation; Probable Erosion - focally stripped)
 - 2 (Unequivocal erosion)
 - 3 (Ulcer or granulation tissue)
- Lamina propria neutrophils RHI subscore and neutrophils in epithelium RHI subscore, categorically (> 0 and > 0, > 0 and 0, 0 and > 0, 0 and 0, respectively)
- Geboes score
 - 0 (architectural changes)
 - 1 (chronic inflammatory infiltrate)
 - 2 (lamina propria neutrophils)
 - 3 (neutrophils in epithelium)
 - 4 (crypt destruction)
 - 5 (erosions or ulcerations)

Baseline histologic activity will also be presented in a by-subject data listing.

6.5. UC Treatment History

UC treatment history will be summarized as the number and percentage of subjects with any prior use of the following medication types since UC diagnosis, including information on specific medications taken for each medication type:

- Aminosalicylates;
- Corticosteroids; and
- Immunomodulators.

The number and percentage of subjects with prior failure to respond and/or prior intolerance, with prior failure to respond, and with prior intolerance will be summarized for each of the above medication types.

Ulcerative colitis treatment history will also be presented in a by-subject data listing.

6.6. Medical History

Medical history (including surgical history) will be coded using the Medical Dictionary for Regulatory Activities (MedDRA) version 24.0 or later. Medical history will be summarized by SOC and PT, with sorting by the internationally agreed order for SOC, and by decreasing frequency and then alphabetically for PT within SOC in the overall column. Counting will be at the subject level for each level of summarization (eg, any medical history, SOC, and PT), with subjects experiencing more than one occurrence of a SOC or PT counted only once.

Medical history will also be presented in a by-subject data listing.

6.7. Prior and Concomitant Medications

Prior medications are defined as all medications that started prior to the date of first dose of PCP study treatment. Concomitant medications are defined as all medications that started on or after the date of first dose of PCP study treatment or that started prior to the date of first dose of PCP study treatment and stopped on or after the date of first dose of PCP study treatment or are ongoing at any time during the PCP. A medication may be considered as both prior and concomitant (ie, prior and concomitant medications are not mutually exclusive).

In general, if it is not clear whether a medication is prior and/or concomitant due to missing or incomplete medication start and/or stop dates, the medication will be considered to be prior and/or concomitant for the given analysis, unless the non-missing portions of the medication start and/or stop dates indicate otherwise.

For subjects who consent to version 2.0 of the protocol, in cases where a medication has a non-missing start date equal to the date of PCP Week 12, the medication will be considered concomitant for the PCP Week 12 Analysis if it is reported on the appropriate concomitant medication eCRF intended to capture medications through PCP Week 12. If the date of PCP Week 12 is missing, then the target day for PCP Week 12 (Day 85) will be utilized for the purpose of determining concomitancy.

In cases where a medication has a non-missing start date equal to the date of first dose of OLE study treatment, the medication will be considered concomitant to the PCP if it is reported on the appropriate concomitant medication eCRF(s) intended to capture medications in the PCP.

Verbatim prior and concomitant medication terms will be coded to a drug class (anatomical therapeutic chemical classification level 2 [ATC2]) and preferred name using World Health Organization (WHO) Drug Global B3 March 2021 or later.

Separate summaries will be presented for prior medications and concomitant medications. Counting will be at the subject level for each level of summarization (eg, any medication, drug class, and preferred name), with subjects receiving more than one medication counted only once.

Prior and concomitant medications will also be presented in a by-subject data listing and will include an indicator, identifying each medication as prior and/or concomitant.

Concurrent procedures such as colectomy and ostomy will be presented in a separate by-subject data listing.

6.7.1. Concomitant Background UC Medications

Concomitant background UC medications at baseline will be summarized as the number and percentage of subjects with concomitant use of aminosalicylates and concomitant use of systemic corticosteroids at baseline, including specific medications taken for each medication type.

The number and percent of subjects who are steroid-free at PCP Week 36, defined as not requiring any treatment with a systemic corticosteroid for a minimum duration prior to PCP Week 36, will be evaluated in the subset of subjects in the ITT population with an actual stratification value of yes for systemic corticosteroid use at baseline. Two different minimum durations will be evaluated, 2 weeks and 4 weeks. Steroid-free duration prior to PCP Week 36 may be summarized continuously as well.

7. EXTENT OF EXPOSURE, COMPLIANCE, AND TIME ON STUDY

7.1. Duration of Study Treatment

Duration of PCP study treatment will be summarized, both as a continuous parameter (in units of days and weeks, as well as total number of subject-years) and as a categorical parameter as follows:

- PCP Week 12 Analysis
 - < 2 weeks, < 4 weeks, ≥ 2 weeks, ≥ 4 weeks, ≥ 8 weeks, ≥ 11 weeks, 2 days (which is the beginning of the protocol-specified visit window for the PCP Week 12 visit), and ≥ 12 weeks
- PCP Final Analysis
 - The above categories for the PCP Week 12 Analysis, plus ≥ 18 weeks, ≥ 24 weeks, ≥ 35 weeks, 2 days (which is the beginning of the protocol-specified visit window for the PCP Week 36 visit), and ≥ 36 weeks

Other categories of duration of PCP study treatment may be utilized for summary purposes as needed.

Duration of PCP study treatment in days will be calculated for the PCP Week 12 Analysis as follows:

- For subjects who consent only to protocol version 1.0 and for subjects who consent to protocol version 2.0 and do not complete PCP Week 12 on study treatment:
 - If the subject's time of last dose of PCP study treatment is prior to 12:00 noon: Date of last dose of PCP study treatment – Date of first dose of PCP study treatment + 0.5
 - If the subject's time of last dose of PCP study treatment is after 12:00 noon or is missing: Date of last dose of PCP study treatment – Date of first dose of PCP study treatment + 1.
- For subjects who complete PCP Week 12 on study treatment:

- If the subject received in clinic dosing at the PCP Week 12 nominal visit: Date of PCP Week 12 nominal visit – Date of first dose of PCP study treatment + 0.5 (due to the last dose of PCP study treatment as of the PCP Week 12 visit being administered per protocol as a morning dose in clinic at the PCP Week 12 nominal visit)
- If the subject had a PCP Week 12 nominal visit but did not receive in clinic dosing at the PCP Week 12 nominal visit:
 - If the subject did not continue dosing in the PCP beyond the PCP Week 12 nominal visit:
 - If the subject's time of last dose of PCP study treatment is prior to 12:00 noon: Date of last dose of PCP study treatment – Date of first dose of PCP study treatment + 0.5
 - If the subject's time of last dose of PCP study treatment is after 12:00 noon or is missing: Date of last dose of PCP study treatment – Date of first dose of PCP study treatment + 1
 - If the subject continued dosing in the PCP beyond the PCP Week 12 nominal visit:
 - Date of PCP Week 12 nominal visit – Date of first dose of PCP study treatment
- If the subject has a missing date for the PCP Week 12 nominal visit, then duration of PCP study treatment will be imputed to 84.5.

Duration of PCP study treatment in days will be calculated for the PCP Final Analysis as follows:

- If the subject entered OLE and the subject's date of last dose of PCP study treatment is the same as the subject's first dose of OLE study treatment: Date of last dose of PCP study treatment – Date of first dose of PCP study treatment + 0.5
- If the subject entered OLE and the subject's date of last dose of PCP study treatment is not the same as the subject's first dose of OLE study treatment, or if the subject did not enter OLE:
 - If the subject's time of last dose of PCP study treatment is prior to 12:00 noon: Date of last dose of PCP study treatment – Date of first dose of PCP study treatment + 0.5
 - If the subject's time of last dose of PCP study treatment is on or after 12:00 noon or is missing: Date of last dose of PCP study treatment – Date of first dose of PCP study treatment + 1

Duration of study treatment will also be presented in a by-subject data listing.

7.2. Compliance

Compliance will be assessed using the following formula:

Compliance (%) = (Number of actual tablets taken/Number of expected tablets) x 100,

where:

Number of actual tablets taken = (Number of tablets dispensed – Number of tablets returned); and Number of expected tablets is based on actual duration of study treatment as described in [Section 7.1](#).

Compliance will be calculated using two different parameters, for which the determination of the number of expected tablets differs. The first parameter, termed compliance with prescribed PCP study treatment, will be calculated taking into account prescribed dose modifications to calculate the number of expected tablets; that is, the number of prescribed tablets will be used as the value for the number of expected tablets. This first parameter represents the extent to which a subject complies with prescribed PCP study treatment. The second parameter, termed compliance with randomized PCP study treatment, will be calculated without taking into account prescribed dose modifications to calculate the number of expected tablets. This second parameter therefore represents the extent to which a subject adhered to randomized PCP study treatment.

Compliance will be summarized using descriptive statistics and categorically (eg, < 80%, ≥ 80 - 100%, > 100 - < 120%, ≥ 120%). Further analyses of compliance may be performed according to compliance with tablets versus delayed-release tablets.

Compliance will also be presented in a by-subject data listing. In addition, IP accountability including bottle information will be presented in a by-subject data listing.

7.3. Prescribed Dose Modifications

Provisions for permitted prescribed dose modifications of IP are described in [Protocol Section 6.5.1](#).

The number and percentage of subjects with a prescribed dose modification, defined as the occurrence of a prescribed dose reduction or prescribed dose interruption, will be summarized.

Subjects with occurrence of a prescribed dose modification will be summarized according to:

- Reasons for prescribed dose modification (liver chemistry abnormality, treatment-related AE other than liver chemistry abnormality, and other).
- Prescribed dose modification type:
 - Those who had only a first step prescribed dose reduction (defined as a reduction in IP dose by 2 tablets BID to a total of 6 tablets BID), and those who had a second step prescribed dose reduction (defined as a further reduction in IP dose by 1 tablet BID to a total of 5 tablets BID).
 - Those who had a prescribed dose interruption.
- Prescribed dose resumption following a prescribed dose modification:
 - Those who resumed a higher dose.

- Those who resumed the original dose.
- Completion of PCP study treatment following a prescribed dose modification:
 - Those who completed PCP study treatment following a prescribed dose modification, broken down by those who completed at a reduced dose versus those who completed at the original dose.
 - Those who discontinued PCP study treatment following a prescribed dose modification.

For the PCP Week 12 Analysis, this will be summarized with respect to completion of PCP Week 12 on study treatment, and for the PCP Final Analysis, this will be summarized with respect to completion of PCP Week 12 on study treatment and completion of PCP on study treatment.

- Duration of prescribed dose modification, defined as time in days from the start of a prescribed dose modification to resumption of original dose (for subjects who resume original dose) or to last dose of study treatment (for subjects who do not resume original dose at time of last dose). For subjects with multiple occurrences of prescribed dose modification, the total duration of prescribed dose modification will be summarized.

Prescribed dose modification information will also be presented in a by-subject data listing.

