
 Immediately interrupt IP. Report the event to the Sponsor's Medical Monitor (or designee) within 24 hours. Repeat liver chemistry tests (include ALT, AST, GGT, ALP, total bilirubin, direct bilirubin, and INR) and perform the Liver Safety Laboratory Assessments (Table 5) within 24 hours. If the repeat liver chemistry test confirms the criteria are met, monitor the subject until liver chemistry test abnormalities resolve, stabilize, or return to baseline after discussion with the Sponsor's Medical Monitor (or designee) (see MONITORING). Do not restart IP unless Sponsor's Medical Monitor (or designee) approval is granted. If restart is granted, IP may be restarted at modified dose (Section 6.5.1). If restart not granted, permanently discontinue IP and continue subject in the study for any protocol specified follow up assessments. Complete an SAE data collection tool if the event also met the criteria for an SAE.^b Liver imaging (ultrasound, magnetic resonance, or computerized tomography), liver biopsy, and/or specialist consultation to evaluate liver disease may be requested by the Sponsor. 	
MONITORING	
If ALT or AST $\geq 3 \times$ ULN AND bilirubin $> 2 \times$ ULN or INR > 1.5:	If ALT or AST $\geq 3 \times$ ULN AND bilirubin $\leq 2 \times$ ULN and INR ≤ 1.5:

 Monitor subject twice weekly until liver chemistry test abnormalities resolve, stabilize, or return to baseline. 	
 Monitor subjects weekly until liver chemistry abnormalities resolve, stabilize, or return to baseline.

^a Serum bilirubin fractionation should be performed if testing is available. If serum bilirubin fractionation is not immediately available, discontinue IP if ALT or AST $\geq 3 \times$ ULN **and** bilirubin $> 2 \times$ ULN. Additionally, if serum bilirubin fractionation testing is unavailable, **record the absence/presence of detectable urinary bilirubin on dipstick** which is indicative of direct bilirubin elevations suggesting liver injury.

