3.3. Standard Calculations

Standard calculations are described as follows:

Age:

Either date of birth or age at informed consent (as an integer) is collected in the IRT system for a given subject. If date of birth is collected, age at time of first dose of PCP study treatment will be calculated in years as $[(\text{date of first dose of PCP study treatment} - \text{date of birth} + 1)]/365.25$, rounded down to the nearest integer. If age at informed consent is collected, age at time of first dose of PCP study treatment will be set equal to the reported age at informed consent.

Change/Percent Change from Baseline:

Change from baseline will be calculated as: Value at post-baseline visit – value at baseline.

Percent change from baseline will be calculated as: $(\text{Change from baseline}/\text{value at baseline}) * 100\%$.

If the value at baseline is 0, percent change from baseline will be missing.

Study Day:

Study day will be calculated as follows:

Date of assessment – Date of first dose of PCP study treatment, where date of assessment is prior to the date of first dose of PCP study treatment

Date of assessment – Date of first dose of PCP study treatment + 1, where date of assessment is on or after the date of first dose of PCP study treatment.

Duration:

Where needed, the duration between two dates Date1 and Date2 will be calculated as follows:

Date2 – Date1 + 1, when expressed in days

$(\text{Date2} - \text{Date1} + 1)/7$, when expressed in weeks.

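### SAP 7.3 ends every unreversed dose modification at the last dose, which cannot measure an interruption that is never restarted

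*SAP*

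**What the plan says.** SAP 7.3 puts reductions and interruptions under one heading: a prescribed dose modification is "defined as the occurrence of a prescribed dose reduction or prescribed dose interruption". Both then share one duration rule. It is "defined as time in days from the start of a prescribed dose modification to resumption of original dose" for subjects who get back to full dose, "or to last dose of study treatment (for subjects who do not resume original dose at time of last dose") for the rest. Where a subject has several episodes they are added up: "For subjects with multiple occurrences of prescribed dose modification, the total duration of prescribed dose modification will be summarized". A by-subject listing of dose-modification information is also planned.

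The SAP's general day count is in section 3.3: "Date2 – Date1 + 1, when expressed in days". It applies where a duration between two dates is needed; SAP 7.3 does not cite it.

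The protocol allows for an interruption that becomes permanent. In Appendix 7, Table 7, the first action is "Immediately interrupt IP". Restart needs approval, and "If restart not granted, permanently discontinue IP and continue subject in the study for any protocol specified follow up assessments". SAP 7.3 expects this kind of ending too, since one of its summary lines counts "Those who discontinued PCP study treatment following a prescribed dose modification".

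Neither document gives another end date for an interruption that is never restarted, a floor at zero, or a rule that such a case counts only as a discontinuation.

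**The concern.** A reduction changes the number of tablets but dosing goes on, so the last dose comes after the start and the interval is meaningful. An interruption stops dosing. If it is never lifted, the last dose is already in the past, or at the latest on the same day, when the interruption begins. The end date is then no later than the start date, and the result is not a length of time off or below the original dose.

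At stake is whether the reported durations can be interpreted. Zero or negative values would enter the descriptive statistics and, because episodes are summed within a subject, could cancel days of genuine modification recorded earlier. Without a written rule, the programmer would have to decide what to do with impossible values.

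**Working it through.** The plan states no figure that depends on this rule, so there is nothing to reproduce. The check applies the rule to example dates. The day numbers are assumed; only the rule comes from the SAP.

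Let S be the recorded start of the modification and L the date of the last dose. Because SAP 7.3 does not say which day count it uses, both are shown: L − S + 1 (SAP 3.3) and L − S (plain elapsed days).

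**Where the rule works**

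- Reduction from Day 40, never reversed, last dose Day 85: 85 − 40 + 1 = 46, or 85 − 40 = 45 days.
- Interruption from Day 41, restarted at a reduced dose, last dose Day 85: 85 − 41 + 1 = 45, or 85 − 41 = 44 days.

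**Where it fails: interruption never restarted at any dose**

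No dose follows the start date, so L ≤ S. Hence L − S + 1 ≤ 1 and L − S ≤ 0, whatever the true time off drug.

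The table takes L = Day 40. The last two columns add an earlier reduction from Day 20, with the original dose resumed on Day 30, which contributes 30 − 20 + 1 = 11 or 30 − 20 = 10 days.

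| Start S | L − S + 1 | L − S | Subject total, +1 count | Subject total, plain count |
|---|---|---|---|---|
| Day 40 | 1 | 0 | 11 + 1 = 12 | 10 + 0 = 10 |
| Day 41 | 0 | −1 | 11 + 0 = 11 | 10 − 1 = 9 |
| Day 42 | −1 | −2 | 11 − 1 = 10 | 10 − 2 = 8 |
| Day 43 | −2 | −3 | 11 − 2 = 9 | 10 − 3 = 7 |

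The only positive value is 1 day, when the interruption carries the same date as the last dose and the +1 count is used (for example, morning dose taken and evening dose withheld). In every other row the permanent interruption contributes zero or less. From Day 42 on, it reduces the subject's total below the 11 or 10 days already accrued, under either count. The values depend only on the gap between last dose and recorded start, not on how long the subject stayed off drug.

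**The case against.** **Recording is not shown.** The problem arises only if a stop that is never lifted is kept in the data as an interruption with its own start date. The documents do not include the eCRF rules. The liver pathway is itself worded in two ways: Protocol 6.5.1 speaks of discontinuing IP for confirmed elevations that meet the Table 7 criteria, whereas Table 7 starts with interruption and a possible restart. Those passages need to be reconciled. Under the former wording a subject might be recorded only as a discontinuation, with no modification duration. This stands as a condition on the point.

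**The last dose may be a deliberate on-treatment cut-off.** SAP 7.1 generally ends treatment duration at the last dose, so days after it could be regarded as off treatment and not as days at a modified dose. A value near zero would then be coherent. But the rule does not deliver a consistent zero: it gives 1, 0 or a negative number according to how the start is dated, and a negative duration has no reading as on-treatment time.

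**Larger negative values reflect dating.** Under the +1 count, a value below zero needs a start recorded two or more days after the last dose, which a data check might catch. That is fair, but a next-day start already gives 0, or −1 by plain subtraction.

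**These subjects remain visible.** SAP 7.3 counts discontinuations after a modification, SAP 5.1 gives discontinuation reasons, and SAP 9.1 tabulates adverse events leading to interruption and to discontinuation separately. This stands, although the SAP 7.3 count does not separate interruptions from reductions.

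**Stronger readings.** A reader might infer that the arm with more permanent interruptions would look better, or that the most serious cases are being minimised. The documents do not support either. They give no expected number of such cases in any arm, plan no between-arm test of this duration, and list among the Table 7 interruption criteria the inability to monitor a subject weekly, so a permanent interruption need not mark the worst clinical outcome. Nor does the rule touch the efficacy results: the treatment-failure rule in SAP 8.1.4 uses discontinuation of study treatment, not the duration of a modification.

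**Conclusion.** The rule is wrong as written for one class of case: a prescribed interruption never restarted at any dose and recorded as an interruption. Its duration is then at most 1 day and usually zero or negative, and it can lower the subject's total. Reductions never reversed, and interruptions restarted at a reduced dose, are handled properly.

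The consequence is small. It is confined to the descriptive dose-modification summary and any listing of these durations. How many subjects would be affected cannot be estimated from the documents. The conclusion rests on two assumptions: that the eCRF keeps such a case as an interruption, which fits the SAP 7.3 wording, and that its start is dated on or after the last dose, which follows from dosing having stopped.

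**What to change.** In SAP 7.3, replace the single end-date rule with text to this effect:

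> Duration runs to the last dose only for dose reductions, and for interruptions restarted at a reduced dose, that are not returned to the original dose. A prescribed interruption after which no further dose is taken is counted in a separate row, interruption followed by discontinuation of study treatment, and that interruption is left out of the duration statistics and of the subject's total. The number left out is shown.

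Earlier modifications in the same subject still count. The same paragraph should say whether the SAP 3.3 day count applies.

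An alternative is to end the interval at the decision to stop permanently. It is less secure: Protocol 7.1 says that the reason for discontinuation is recorded, but the documents do not show that a decision date is captured, and the interval would partly measure how long the decision took.

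The cost is a short SAP edit and a small programming change. The downside is that these interruptions contribute no duration, which is why their number should be stated beside the summary.
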